6. STUDY PROCEDURES

A Schedule of Evaluations is provided in section 6.1 below.

6.1 Schedule of Evaluations

Assessment	Phone Pre- Screen	Screening Visit	Baseline Visit 1	Baseline Visit 2	10 days Post- Biopsy Visit	30- Day Visit	60- Day Visit	90- Day Visit 1	90-Day Visit 2	10 days Post- Biopsy Visit	Follow- up 30 Day
Telephone interview prescreening	X										
Informed Consent		X									
Informed Consent for Data/Tissue Bank (optional)			X								
Medical history (inclusion/excl usion criteria)		X									
Medical History Update			X	X	X	X	X	X	X	X	X
Height (without shoes)		X									
Physical Exam		X									
Mini-Mental Status Exam (MMSE)		X									
Center for Epidemiologic Studies - Depression Scale (CES-D)		X									
Weight/Girth Measurement		X	X			X	X	X			
CMP & CBC w/Diff		X	X	X	X	X	X	X	X	X	X
Inflammation Markers in blood			X					X			
Vitals (blood pressure + heart rate)		X	X	X	X	X	X	X	X	X	X
Short Physical Performance Battery (SPPB)		X	X					X			
Physical Function (6 min walk test)			X					X			
Activity Monitor			X					X			

Biodex (knee extension and flexion)		X					X			
Muscle Biopsy			X					X		
Randomization			X							
Product Dispense			X		X	X				
Product Compliance					X	X	X			
Adverse Event Assessment Toxicity (NCI) criteria		X	X	X	X	X	X	X	X	X

6.2 Description of Evaluations

Telephone interview pre-screen: Potential participants will undergo an initial telephone pre-screening to assess inclusion and exclusion criteria, which will include a brief medication and health history.

Informed consent: Potential participants will first provide informed consent to participate in this study. The study coordinator will explain to prospective participants the purpose, methods, and extent of the study. Potential participants will be asked to read the informed consent form and to ask questions. The research assistants will review all key aspects of the study verbally, and will then ask several questions to ascertain whether potential participants have understood the information. Two copies of the consent form are to be made, one for the participant and one for the investigators to be stored in the participant's individual file.

Informed consent to participate in the Tissue/Data Bank, PI – [name]: Study participants will be asked if they agree that left-overs from the blood and muscle samples can be stored in the bank and used for future research. The research assistants will review all key aspects of the study verbally, and will then ask several questions to ascertain whether potential participants have understood the information. Two copies of the consent form are to be made, one for the participant and one for the investigators to be stored in the participant's individual file.

Medical history (inclusion/exclusion criteria): The information to be collected includes basic demographic and lifestyle factors including living situation, ethnicity and language, personal medical history, smoking history, alcohol use, known allergies, medication history, and level of education.

Medical history update: The information to be collected includes any changes in health status and/or medications.

Physical Exam: The physical exam consists of a medication inventory, medical and hospital admission history, a review of the telephone screen, a Mini Mental Status Exam (MMSE), and a physical exam including height, blood pressure, radial pulse, weight, waist circumference, and hip

circumference. Blood pressure and heart rate will be measured twice in the seated position following 5 minutes of rest using an oscillometric device. Height will be measured without shoes standing against a wall using a calibrated stadiometer. Body Mass Index will be calculated as the quotient of the participant's weight in kilograms by the square of their height in meters. In addition, participants will meet with a health care provider (study physician, nurse practitioner, or physician's assistant) for a brief physical exam of overall health and wellness.

Mini-Mental Status Exam (MMSE): The MMSE is a widely used and well-validated brief screening tool that is used to screen for cognitive impairment. It measures orientation to time and place, immediate recall, short-term verbal memory, calculation, language and construct ability.

Center for Epidemiologic Studies - Depression Scale (CES-D): The CES-D is a brief questionnaire that measures depressive feelings and behaviors during the past week. It is a self-administered screening measure developed to identify current depressive symptomatology related to major or clinical depression in adults.

Weight/Girth Measurement: Weight will be measured following the removal of excess clothing and with calibrated scales. Girth measurements will include measurements at the abdomen and hip area. The waist measurement is taken at the visually narrowest waist level of the participant, or if this is not apparent, at the mid-point between their lowest rib and the top of their hip bone. Waist circumference will be measured according to the NHANES III Protocol (http://www.ncbi.nlm.nih.gov/books/bv.fcgi?rid=obesity.box.236). The hip girth measurement is taken over minimal clothing, at the level of the greatest protrusion of the clients gluteal (buttock) muscles. The participant stands erect with their weight evenly distributed on both feet and legs slightly parted, making sure that they do not tense their gluteal muscles.

CMP & CBC with Differentials: Fasting blood samples will be taken (analyzed by CLIA certified Laboratories) for a Comprehensive Metabolic Panel (CMP) and Complete Blood Count (CBC) with Differential.

Inflammation Markers: Blood samples will be taken to measure levels of inflammatory markers.

Short Physical Performance Battery (SPPB): The SPPB is designed to assess lower-extremity function by measuring three timed subtests: five timed repetitive chair stands, standing balance (i.e. hold tandem and semi-tandem foot position for 10 seconds), and gait speed during a 4 m walk at one's usual pace. Each subtest is scored from 0 to 4, with 0 indicating inability to complete test, and 4 indicating maximal performance. A summary score from 0 to 12 is calculated for the SPPB, where higher scores indicate better physical function.

Physical Function (6 min walk test): The 6 Minute Walk test measures the amount of distance the participant can complete on a standard walking course in six minutes without running or overexerting themselves.

Activity Monitor: Participants will also be instructed in the use of an activity monitor that they will be asked to wear for 24 hours for seven days and then return at their next visit. The monitor estimates energy expenditure by combining data from a tri-axial accelerometer with galvanic skin response, skin temperature, and heat flux.

Biodex (knee extension and flexion): This test involves using an isokinetic dynamometer set at 90 degrees per second. Participants will perform 50 maximal knee extension and flexion concentric repetitions, which will be administered by trained and certified research assistants.

Muscle Biopsy: Skeletal muscle samples will be obtained under local anesthesia from the *vastus lateralis* muscle using a percutaneous needle biopsy technique as previously described by our group[62] (see **Appendix 1** for detailed description of procedure). The skin will be closed using steri-strips.

Randomization: The randomization will be performed using the CTSI's standard methodology for double blind randomization.

Product Dispense: Up to a A 40-day supply of study product (i.e. placebo [vegetable cellulose] or resveratrol [1000 mg/day or 1500 mg/day]) will be provided in person to the participant at the conclusion of their baseline biopsy, 30-day, and 60-day clinic visit.

Product Compliance: All medication containers, whether empty or containing unused tablets, must be collected to allow medication compliance to be determined (via a pill count) and to allow for proper destruction of the medication. Compliance will be measured by the number of pills returned at the visit compared to the number expected with 100% compliance. The research assistant will discuss the participant's adherence to medication since the previous clinic visit.

Adverse Event (AE) Assessment Toxicity (NCI) Criteria: At the designated intervals for event collection, participants will be asked the following question: "Since your previous visit, were you diagnosed with any new disease or condition, or experienced significant worsening of the diseases you were previously diagnosed with?" AEs will be obtained by self-report and will not require supporting documentation. AEs will be reported quarterly to the Independent Safety Board (oversight committee) and the NCCIH for each blinded treatment group.

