4.2 Exclusion Criteria

All candidates meeting any of the exclusion criteria listed below at baseline will be disqualified from study participation.

- Non-English speaking individual.
- Failure to provide informed consent;
- Allergy/sensitivity to grapes or Japanese knotweed;
- Current dietary supplementation of grape seed extract or ginko biloba;
- Consumption of ≥ 8 oz. of red wine/dealcoholized red wine/red or purple grape juice more than once weekly;
- Consumption of any dietary supplements containing resveratrol, quercetin, or *P. cuspidatum* in the previous 90 days;
- Active treatment for cancer, stroke (< 6 months), peripheral vascular disease, coronary artery disease, myocardial infarction (< 6 months), congestive heart failure (stage III or IV), valvular heart disease, major psychiatric disease, severe anemia (blood levels of Hemoglobin < 8 g/dl), bleeding disorders or other blood disorders, liver or renal disease, diabetes, severe osteoarthritis, blindness or deafness, fracture in upper or lower extremity (< 6 months), upper or lower extremity amputation, or Parkinson's disease;

- Cognitive impairment (i.e. Mini Mental Status Exam ≤ 23);
- History of significant head injury that currently interferes with functioning;
- Severe physical limitations (i.e., < 4 on the Short Physical Performance Battery);
- Hard exercise (i.e. running, bicycling, etc.) ≥ 30 min on five or more days per week;
- Excessive alcohol use (> 2 drinks/day) or alcohol abuse (> 5 drinks/day for males, or > 4 drinks/day for females);
- History of substance abuse within the past six months;
- Mood disorder (i.e. Center for Epidemiological Studies Depression (CES-D) ≥ 16);
- History of tobacco use within the past three years;
- Resting heart rate > 120 bpm at screening visit;
- Systolic blood pressure > 160 mm Hg at screening visit;
- Diastolic blood pressure > 90 mm Hg at screening visit;
- Fasting glucose ≥ 126 mg/dL at screening visit;
- Abnormalities in blood chemistry parameters, defined by blood chemistry marker outside of healthy range) as determined by study physician;
- Current use of
 - o anabolic treatments (e.g. growth hormone or testosterone),
 - o anticholinesterase inhibitor (e.g. Aricept),
 - o hormone replacement (e.g. Estrogen),
 - o anticoagulant therapies (note: aspirin -anti-platelet use (≤ 81 mg/day) is permitted) or
 - o use of anti-inflammatory medications more than 3 times per week

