4.3 Study Enrollment Procedures

Recruitment. We will use multiple resources for recruiting our participants that include those originating at the Department level, but also the UF Clinical Translational Science Institute (CTSI). We have a wealth of experience recruiting high and moderate functioning older adults, which will suit this study well. We have a subject pool of 43 individuals with low-to-high functioning physical characteristics (N=43) who participated in the pilot study described above, as well as a registry of over 2,240 participants, out of which 69.4% are over the age of 70. Thus, we have a good initial base of potential participants to be recruited for the present study. Additional participants, if needed, will be enrolled from the North/Central Florida region. The North/Central Florida region includes Gainesville (home to the University of Florida), its home county (Alachua), and the eight immediately surrounding counties (Bradford, Clay, Columbia, Gilchrist, Levy, Marion, Putnam, and Union). The total population of older adults falling within the target age range in these counties is 216,217. We recognize that fewer people may be interested in a study involving muscle biopsies due to the relatively invasive nature of the biopsy procedure. Given the current demographics of North/Central Florida, the fact that we have a large base of potential participants already identified, and that this is an intervention study, we do not anticipate difficulties with the enrollment of 60 subjects. Moreover, there were no untoward outcomes associated with completed muscle biopsies on participants in our previous pilot studies. Thus, we do not anticipate difficulty obtaining our proposed sample size of 60 participants.

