9.5.2 Secondary Outcomes

Resveratrol supplementation is also hypothesized to increase the following secondary outcomes: (1) PGC-1 α (primary outcome), AMPK, SIRT1, and SIRT3 levels in muscle specimens obtained from the *vastus lateralis*. See **Table 4** below:

Table 5. Evaluation of the Effect of Resveratrol on Outcome Measures

	Measures	Comments
Highest priority for Aim #1	Respiration, COX and CS, Mt DNA content	Respiration analysis will also provide information on the ability to metabolize fatty acids. COX and CS are quantitative measures of oxidative metabolism. CS correlates with mitochondrial volume. COX correlates with overall mitochondrial function.
Highest priority for Aim #2	PGC-1α, SIRT1, SIRT3, AMPK	PGC-1α promotes mitochondrial biogenesis and improves muscle performance. SIRT1 is mainly implicated as an activator of PGC-1α, with only select reports on SIRT3, a mitochondrial sirtuin.
Exploratory Aim #3	Functional assessment or walking speed, muscle fatigue and SPPB	We and others have shown that CS, COX, and PGC - 1α, correlates very well with functional assessments of walking speed.

The secondary outcomes listed in the table above will be assessed at the second baseline visit, and at the second follow-up visit. The Exploratory outcomes related to changes in physical function will be assessed at the first baseline visit, and the first follow-up visit.

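### The SPPB summary is a rounded score capped at 12 with no upper entry limit and no ceiling handling; adding chair-stand time and 4 m gait speed beside it would sharpen an exploratory outcome cheaply

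*Combined protocol and SAP*

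**What the plan says.** Section 6.2 describes the SPPB as "measuring three timed subtests: five timed repetitive chair stands, standing balance" and a 4 m walk at usual pace. On scoring it says: "Each subtest is scored from 0 to 4, with 0 indicating inability to complete test, and 4 indicating maximal performance". The total follows: "A summary score from 0 to 12 is calculated for the SPPB, where higher scores indicate better physical function". The schedule in 6.1 places the SPPB at screening, the first baseline visit and the first 90-day visit.

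Section 4.2 excludes people scoring "< 4 on the Short Physical Performance Battery". There is no upper SPPB limit. On recruitment, section 4.3 says: "We have a wealth of experience recruiting high and moderate functioning older adults, which will suit this study well".

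Table 5 in section 9.5.2 lists the exploratory function measures as "Functional assessment or walking speed, muscle fatigue and SPPB". Sections 1.2 and 9.1 give higher walking speed, better physical performance and greater resistance to fatigue as separate exploratory hypotheses.

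Section 9.2 plans a linear mixed model for secondary variables with repeated measures, with t-tests on change as a sensitivity analysis. It mentions neither a bounded score nor the SPPB component times.

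**The concern.** A total of 12 needs the top category on all three subtests (3 × 4 = 12). Someone who starts there and becomes faster still scores 12. The recorded change can only be zero or negative, whatever the treatment does.

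The entry rules remove people at the bottom of the scale and leave the top open. The more participants start at or close to 12, the more a real effect on mean change is diluted. A null SPPB comparison could then mean no effect or no room to improve, and the plan gives the reader no way to tell which. The quantities that would help, chair-stand time and 4 m gait speed, have to be timed anyway to assign the score.

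**Working it through.** **What follows from the scale alone.** The largest possible gain is 12 minus the baseline score: 0 at 12, 1 at 11, 2 at 10. No assumption is needed.

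**The plan's own figure.** None is given for SPPB: no mean, SD, target difference or share at 12. The only power statement (section 9.2: 18 completers per arm, correlation 0.7, 80% power for 0.69 SD) concerns State 3. With those inputs the SD of change is √(2 × (1 − 0.7)) = 0.775 SD, and the contrast has standard error 0.775 × √(1/18 + 1/36) = 0.224 SD. The difference detectable at 80% power by noncentral t (51 df) is then 0.64 SD, so the stated 0.69 is on the cautious side. This does not bear on SPPB.

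**Inputs for the illustration.** From the plan: 18 per arm, the average of the two active arms against placebo, two-sided 0.05, Satterthwaite correction, change from baseline, and correlation 0.7 (stated for State 3). Assumed: latent score SD 1.8 points, true gain 0.85 points in both active arms, and correlation 0.8 as an alternative.

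**Uncapped benchmark.**
- Correlation 0.8: SD of change 1.8 × √0.4 = 1.138; standard error 1.138 × 0.2887 = 0.329; 0.85/0.329 = 2.59. Simulated power is 71%.
- Correlation 0.7: SD of change 1.8 × √0.6 = 1.394; standard error 0.402; 0.85/0.402 = 2.11. Simulated power is 53%.

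**Capped score.** Latent baseline and 90-day scores are drawn, rounded to whole points and cut to 0–12, and the contrast is tested on change. A baseline of 12 is recorded when the latent value reaches 11.5. A latent mean of 9 therefore gives P(Z > 2.5/1.8) = 8% at 12, and a mean of 10.5 gives P(Z > 1.0/1.8) = 29%.

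| Share at 12 at baseline | Mean gain seen (true 0.85) | Power, correlation 0.8 | Power, correlation 0.7 |
|---|---|---|---|
| uncapped, unrounded | 0.85 | 71% | 53% |
| 8% | 0.79 | 62% | 47% |
| 29% | 0.62 | about 50% | 38% |

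The gain seen is 0.79/0.85 = 93% and 0.62/0.85 = 73% of the true gain. Monte Carlo error with 8,000 trials is about √(0.5 × 0.5/8,000) = 0.6 points.

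**Separating rounding from the cap.** At correlation 0.8 with only about 3% at 12, power is already 64%. Most of the drop from 71% to 62% in the 8% row is therefore rounding. The further fall to about 50% in the 29% row is mainly the cap.

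**Other assumptions, same direction.** With latent SD 2, correlation 0.7 and a shift of 0.69 SD, power is about 85% uncapped. It falls to 76%, 70% and 63% with 10%, 20% and 30% at 12.

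**Limits of the illustration.** It treats the SPPB as one rounded latent score rather than three summed categories. It tests change scores, not the mixed model. It also takes the uncapped measure to carry the same signal as the latent score.

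**The case against.** Function does not rest on SPPB. Walking speed is a hypothesis of its own, and the six-minute walk and Biodex fatigue are also measured without a score cap. That stands, although Table 5 does not name the six-minute walk, and chair-rise performance enters only through the SPPB.

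The link from the physical-performance hypothesis to SPPB is inferred. So is the link from SPPB to the mixed model, which section 9.2 assigns to secondary variables. Both readings are natural, but neither is written down.

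A reader might infer that the sample will sit largely at the ceiling. The documents do not support that. Section 2.1 names people with slower walking speed as the target, section 3 wants a functionally mixed sample, section 4.3 describes a pilot pool that reaches down to low function, and section 4.2 excludes frequent hard exercisers. None of these is an upper SPPB limit, but together they leave the share at 12 open. A share of half or more would need a latent mean of 11.5 or higher in the illustration, and nothing in the text points there.

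A reader might also infer that anyone near 12 has no room to rise. Only a score of exactly 12 rules out a gain. At 11 a participant can gain 1 point, more than the 0.85 assumed.

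Finally, a reader might conclude that the summary should be demoted to descriptive. That would drop balance from the inferential analysis, and timing cannot rescue balance, because participants "hold tandem and semi-tandem foot position for 10 seconds" and no longer. Keeping a standard summary score as an exploratory outcome is defensible.

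**Conclusion.** The point holds as a modest, inexpensive improvement to an exploratory outcome. The cap, the absence of an upper entry limit and the absence of ceiling handling are all in the text, and attenuation follows from them whenever some participants start near 12.

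Its size cannot be fixed from the documents. On the assumed inputs the loss is 6 to 9 percentage points of power with 8% at 12 (53% to 47%, or 71% to 62%) and 15 to about 21 points with 29% at 12 (53% to 38%, or 71% to about 50%). Part of this is rounding. At the plan's correlation of 0.7 the comparison is weak even without a cap. The State 3 result and the Aim 2 results are untouched, and section 9.2 says that the study is powered around State 3 only.

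**What to change.** In section 9.2 and Table 5:

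- Keep the SPPB summary as an exploratory outcome.
- Add five-chair-stand time (s) and usual-pace 4 m gait speed (m/s) as continuous exploratory outcomes, each adjusted for its baseline value.
- State that 4 m gait speed also serves the walking-speed hypothesis, so that it is not counted as a separate finding.
- Rank participants unable to complete a subtest as worst, and make the comparison that includes them on ranks. The rule is needed: someone scoring 0 on chair stands can still total up to 8 (4 + 4) and pass the entry floor of 4.
- Confirm that the case report form captures the raw times. Section 6.2 says that the subtests are timed, not that the times are kept.
- Report the baseline share scoring 12 by arm, so that a null SPPB result can be read correctly.

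The cost is SAP wording, a check of the case report form, one or two more exploratory comparisons, and the non-completer rule. No visit or test is added. The balance hold stays capped at 10 seconds.

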Potential Risks of the interventions. In our resveratrol pilot study, resveratrol supplementation of 300 mg/day and 1000 mg/day had minimal effects on blood chemistries, and there were no significant differences in the number of participants reporting adverse or toxic events (e.g. headaches) across the three conditions (all p values > 0.05). Noteworthy, the 1000 mg/day dose has been shown to be safe and well tolerated in previous safety trials in young and middle-aged adults. [58-60] Additionally, a recent repeated dosing study found that a dose of 200 mg of resveratrol at eight hour intervals for a three day period was well tolerated by older adults (age \geq 65 years), [61] and similarly, 1000 mg/day of resveratrol supplementation was well tolerated by older adults in a four-week intervention. [56]

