7.3 Adverse Events and Serious Adverse Events

Adverse Event – An adverse event (AE) is defined as any untoward medical occurrence associated with the use of a drug in humans, whether or not considered drug related. An adverse event (also referred to as an adverse experience) can also be any unfavorable and unintended sign (e.g., an abnormal laboratory finding), symptom, or disease temporally associated with the use of a drug, without any judgment about causality. An adverse event can arise from any use of a drug (e.g., off label use, use in combination with another drug) and from any route of administration, formulation or dose, including overdose.

Serious Adverse Event (SAE) - Any AE that results in one or more of the following outcomes:

- Death
- A life-threatening event
- Inpatient hospitalization or prolongation of existing hospitalization
- A persistent or significant disability/incapacity
- A congenital anomaly or birth defect
- An important medical event based upon appropriate medical judgment

Serious adverse events (SAEs) that are unanticipated and/or possibly related to study participation are reported to the NIH within 48 hours of learning of the event, to the IRB and Independent Safety Board (oversight committee) within five business days of learning of the event. If an event, incident, experience, or outcome is life-threatening or fatal, the IRB must be notified by phone within 24 hours.

Any unexpected fatal or life-threatening suspected adverse reactions will be reported to the FDA no later than 7 calendar days after the initial receipt of the information. For SAEs that are not fatal or life-threatening, the time frame for submitting an IND safety report to FDA is no later than 15 calendar days after the investigator-sponsor determines that the suspected adverse reaction or other information qualifies for reporting.

Minor events will be reported to the University of Florida's Health Science Center IRB at the time of annual review, as well as to the oversight committee on a bi-annual basis. Both the principal investigator and the study staff will review the study weekly and examine reports of adverse incidents and reports of study participant recruitment and follow-up. Throughout the course of the study, information regarding issues deemed critical to the study or to the safety of research participants will be provided to the principal investigator and primary mentors. As a result of

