receiving this critical information, a meeting to discuss this critical information may be convened. Information deemed critical would include:

- serious and non-serious adverse events that may occur,
- suspicion of scientific fraud or misconduct,
- any other issues which may warrant protocol changes or modifications.

Monitoring of both AEs and SAEs will be achieved via administration of structured questionnaires. Standardized forms for referring and treating study participants who experience adverse events will be in place.

 Classification of AE Severity – Adverse events will be graded according to Common Terminology Criteria for Adverse Events (CTCAE) v 4.03. The study physician will be responsible for all trial-related medical decisions and the review of AEs throughout the study. The physician will assess AEs and will ensure that they are recorded in detail. Adverse events, whether in response to a query, observed by study team, or reported spontaneously, will be reported on the appropriate CRF and/or source document.

AE Attribution Scale – All adverse events (AEs) will also be categorized according to the likelihood that they are related to the study intervention. Specifically, they will be labeled either definitely, probably, possibly, or unrelated to the study intervention. The classification of potential relationship to the intervention is shown in **Table 2**.

Table 2. Adverse Event (AE) Classification

Adverse Event (AE) Classification		
Definite.	Temporal pattern + known or expected AE response pattern + confirmed by	
	stopping the intervention + reappearance of AE on re-challenge	
Probable.	Temporal pattern + known or expected AE response pattern + confirmed by	
	stopping the intervention + could not be explained by participant's clinical state	
Possible.	Temporal pattern + known or expected AE response pattern + could have been	
	produced by a number of other factors	
Unknown.	Relationship for which no evaluation can be made	
Not related.	AE for which sufficient information exists to indicate that the cause is unrelated	
	to the study intervention	

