9.4 Interim Analyses and Stopping Rules

No interim analyses are planned.

To determine the short and long term toxicities associated with administration of two doses of resveratrol when compared to a placebo in adults aged ≥ 65 years. The incidence, type, and severity of adverse events will be recorded during all phases of treatment and follow-up according to the Schedule of Activities shown in **Table 1**.

A single grade IV toxicity or two grade III toxicities will trigger an off cycle review by the DSMB, who can recommend suspension, amendment, or termination of the trial.

Toxicity due to this therapy is expected to be low. A description of each of the following study endpoints will be made at the conclusion of the subjects' accrual and 90 day post-treatment assessment:

- A. The number of subjects experiencing grades 1-5 adverse events according to Common Terminology Criteria for Adverse Events (CTCAE) v.3.0; the nature of these events; and the timing of their occurrence.
- B. The presence and magnitude of detectable change in blood chemistries.

Participants may have their treatment discontinued (permanently or temporarily) but remain on study for the following reasons; (a) unacceptable toxicity (≥ grade 3 toxicity) related to administration of resveratrol, using the toxicity criteria outlined in **Table 4**; (b) participant non-compliance with the study protocol; or (c) intercurrent disease, medication use, or condition that would affect the assessment of the participant's status. Of course, a participant is free to withdraw from the study at any time.

The study physician ([name]) will advise on whether or not he believes the participant should be removed or temporarily suspended from the study based on the toxicity criteria listed below.

Table 4. Dosage adjustment scheduled based on changes in blood chemistry values or participant report of clinically important symptoms.

Lab	Value	Placebo	Resveratrol 1000mg/day	Resveratrol 1500mg/day
WBC (n/μL)	< 3,000	Temporary Stop	Temporary Stop	Temporary Stop
Platelets (n/μL)	< 50,000	Temporary Stop	Temporary Stop	Temporary Stop
Creatinine Clearance (mL/min)	< 30	Temporary Stop	Temporary Stop	Temporary Stop
AST, ALT	> 2.0x ULN	Temporary Stop	Temporary Stop	Temporary Stop
Hematocrit	< 27%	Temporary Stop	Temporary Stop	Temporary Stop

Lab	Value	Placebo	Resveratrol 1000mg/day	Resveratrol 1500mg/day
Clinically Important Symptoms	Yes	Temporary Stop	Temporary Stop	Temporary Stop

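### The one scripted adverse event question asks about diagnoses, not symptoms, so it is narrower than the plan's own adverse event definition and low-grade symptoms can be undercounted

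*Combined protocol and SAP*

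**What the plan says.** Section 6.2 (Adverse Event Assessment) gives the question to be put at the designated visits: "were you diagnosed with any new disease or condition, or experienced significant worsening of the diseases you were previously diagnosed with". The same paragraph adds that "AEs will be obtained by self-report and will not require supporting documentation". No other adverse event question is worded anywhere in the document. Section 7.3 says that "Monitoring of both AEs and SAEs will be achieved via administration of structured questionnaires", without giving their content.

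The definition in section 7.3 is wider. It extends to "any unfavorable and unintended sign (e.g., an abnormal laboratory finding), symptom, or disease temporally associated with the use of a drug" and requires no diagnosis. Section 9.4 will describe "The number of subjects experiencing grades 1-5 adverse events", so mild events are meant to be counted. Section 2.2 illustrates an adverse event with headache, reporting on pilot "participants reporting adverse or toxic events (e.g. headaches) across the three conditions". Section 7.1 repeats that example, and section 9.2 uses headache as its example of a treatment effect leading to withdrawal.

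Section 9.2 ends by assigning side effects to Fisher's exact test. It does not say which data source supplies the counts.

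**The concern.** The definition and the scripted question do not match. The definition turns on a symptom occurring. The question turns on a diagnosis having been made, or on a diagnosed disease having become significantly worse. Headache or stomach upset that never reached a doctor meets the definition but does not call for a yes.

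The events at risk are mild, self-limiting symptoms. If some go unrecorded, the grade 1 to 5 summary is too low and the comparison between arms loses power, which makes an apparent absence of difference more likely. With 20 participants per arm there is little power to spare. Table 4 in section 9.4 also has a row that depends on participants reporting clinically important symptoms, so the way they are asked matters for more than the final table.

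**Working it through.** The documents give no adverse event rate, no power for side effects and no capture rate, so there is no planned figure to reproduce. The check is mainly one of wording.

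**Step 1. Question against definition.**

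| Case | Event under section 7.3? | Yes to the section 6.2 question? |
|---|---|---|
| New disease, diagnosed | Yes | Yes |
| Diagnosed disease, significantly worse | Yes | Yes |
| Diagnosed disease, slightly worse | Yes | Not required |
| New headache, no doctor seen | Yes | Not required |

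The last two rows are the gap.

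**Step 2. Other routes by which such an event could be recorded.**

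| Route | Section | What it adds | Limit |
|---|---|---|---|
| Diary | 5.1 | Any adverse event, no diagnosis needed | Tied to daily product intake; not in the schedule (6.1) or the visit lists (6.2.4, 6.2.5); none described after treatment |
| Symptom log at each visit | 7.1 | Asks for symptoms; reviewed by staff | Worded in the present tense, so it can miss what resolved between visits |
| Calls from participants | 7.1 | Any event | Depends on the participant's initiative |
| Medical history update | 6.2; schedule 6.1 | Changes in health, from Baseline Visit 1 to the 30-day follow-up | Not specific to symptoms; missing from the 90-day list in 6.2.5 although the schedule marks it |
| Recording rule | 7.3 | Queried, observed and spontaneous events all go on the case report form or source document | Governs known events; does not elicit them |

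Together these routes will catch some or many of the events that the question passes over. None gives a capture fraction.

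**Step 3. What incomplete capture would do (illustration only).** Let p_P and p_R be the true symptom rates on placebo and resveratrol, and c the fraction captured, equal in all arms. The recorded rates are c·p_P and c·p_R. Their ratio is unchanged, but their difference shrinks by the factor c. Power of the two-sided Fisher test at 0.05 is the sum, over all pairs (a, b) with p ≤ 0.05, of Bin(a; n_P, c·p_P) × Bin(b; n_R, c·p_R). The arm size of 20 is from section 3. The rates, the values of c and the pooling of the two active arms (20 v 40) are assumptions.

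| True rates, placebo v resveratrol | Arms | c = 100% | 75% | 50% | 25% |
|---|---|---|---|---|---|
| 10% v 45% | 20 v 40 | 80% | 61% | 36% | 5% |
| 10% v 45% | 20 v 20 | 62% | 43% | 23% | 4% |
| 10% v 40% | 20 v 40 | 67% | 49% | 26% | 3% |
| 10% v 40% | 20 v 20 | 49% | 33% | 17% | 3% |

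Example: at c = 50% with 10% v 45%, the recorded rates are 5% and 22.5%, and power for 20 v 40 falls from 80% to 36%. With a smaller true difference, 10% v 20%, power for 20 v 40 is only 11.5% even at full capture, so sample size is then the main limit.

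**The case against.** The strongest reply is that the scripted question is only one route among several. Section 7.1 names clinical observation of symptoms as the main means of protecting participants and adds the log and the calls. The medical history update needs no diagnosis, is not confined to what is felt on the day, and continues through the post-treatment visits. The recording rule in section 7.3 means that a no to the scripted question does not exclude an event reported another way. All of this stands, and it limits the point.

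A reader might infer that the comparison of side effects between arms is in fact undercounted. The documents do not support that: section 9.2 does not tie the Fisher test to answers to this question, and nothing suggests a particular capture fraction. Nor do they support an inference of bias towards one arm. The question is the same for everyone and participants are blinded, so the expected effect is lost power.

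The link to off-cycle safety review is also weak. Section 9.4 triggers that review on one grade IV or two grade III toxicities, not on the mild symptoms at issue. The symptom row of Table 4 can be reached by any participant report.

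The reply does not remove the mismatch. The only adverse event question that the plan words asks for less than the plan defines. The other routes are open-ended, tied to treatment, confined to the present or dependent on the participant.

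**Conclusion.** The point holds as an inconsistency with a possible effect on safety data. The scripted question is narrower than the definition in section 7.3 and the grade 1 to 5 count in section 9.4, and the plan's own example can pass through it unreported. Low-grade symptoms can be undercounted; whether they are, and by how much, cannot be determined from the documents.

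Any loss should be similar in all arms and would reduce the power of the Fisher comparison. The power figures above show only the direction and the possible scale. They rest on assumed event rates, capture fractions and, for 20 v 40, a pooling of active arms that the plan does not state for this test. The change is worth making because it is cheap and improves safety capture.

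**What to change.** Reword the question in section 6.2 so that, at every adverse event visit including the 10-day and 30-day follow-ups, it asks: since your last visit, have you had any new or worse symptom, illness, injury or health problem, whether or not you saw a doctor? Keep the existing diagnosis question as a follow-on item.

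In section 9.2, state that answers to the question, diary entries, the symptom log, the medical history update and spontaneous reports together form the adverse event dataset for the Fisher test.

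The cost is one reworded form item and one added sentence. The downside is more low-grade events to grade and enter in all arms.
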